#### 3.2 Rationale for Dose Selected

#### 3.2.1 Ivosidenib

Ivosidenib is FDA approved for relapsed refractory IDHI mutated AML. Data have shown ivosidenib to be well tolerated at total daily doses up to 1200 mg in solid tumors (AG120-C-002) and in hematologic malignancies (AG120-C-001}; the MTD was not reached in either study. As of a 16 January 2016,

122 participants have been treated with ivosidenib in the AG120-C-002 study, of which 84 participants received 500 mg QD; 119 participants have been treated with ivosidenib in the AG120-C-001 study, of which 89 participants received 500 mg QD. Based on a review of the available safety, PK/PD, and clinical activity data observed during dose escalation, 500 mg QD was selected as the ivosidenib dose for the expansion phases of both of these trials.

In these studies, there have been minimal dose interruptions, and without an apparent dose relationship for any commonly reported TEAEs or Grade 2:3 TEAEs. No DLTs have been reported in Study AG120-C-002. Dose-limiting toxicities of Grade 3 rash and Grade 3 QT prolongation were observed in the 1200 mg QD and 800 mg QD cohorts respectively in Study AG120-C-001; however, expansion of these dose cohorts did not result in identification of the MTD.

Plasma ivosidenib exposure increased in a less than proportional manner across doses from 100 mg BID

to 1200 mg QD, nearing a plateau at 500 mg QD, in both solid tumors and hematologic malignancies. Sustained and consistent plasma 2-HG inhibition was observed with plasma 2-HG levels reduced to the normal range of healthy volunteers (up to 98.0% inhibition in solid tumors, 99.7% in hematologic malignancies) at all doses, with no apparent dose response. The 500 mg QD dose has shown a maximum PD effect based on 2-HG levels for the majority of participants.

For Study AG120-C-002, efficacy data were analyzed separately based on the underlying disease and specific response criteria: cholangiocarcinoma, chondrosarcoma, or glioma (see Section 5.4.2 in Investigator's Brochure 7.0 for greater detail). As of March 10, 2017, 73 participants with cholangiocarcinoma received ivosidenib in the dose escalation and expansion cohorts, with 62 participants receiving ivosidenib at 500 mg QD. Overall, 5% (n=4) experienced a confirmed partial response and 56% (n=41) experienced stable disease. The 6-month progression-free survival (PFS) rate was 38.5% and the 12-month PFS rate was 20.7%. As of 23 September 2016, 21 participants with chondrosarcoma had been treated with ivosidenib and 20 were efficacy-evaluable. Eleven (55%) participants experienced stable disease as their best overall response; the remaining participants experienced disease progression (30%) or were not assessed (15%). The 3-month PFS rate was 58% with a median ivosidenib treatment duration of 2.6 months (range, 0 to 24 months).

As of May 12, 2017, 66 participants with glioma have been treated with ivosidenib and enrollment of this subset was complete; of these participants, 35 had non-enhancing glioma. Two of these 35 participants (6%) had a minor response according to RANO-LGG. Twenty-nine (83%) participants had stable disease and 4 (11%) had progressive disease as their best response; the median treatment duration for non-enhancing glioma was 16 months with 63% of participants being treated for 1 year. Volumetric analysis (conducted centrally) demonstrated stabilization or a decrease in tumor growth rate compared to the pretreatment rate in glioma participants with non-enhancing disease receiving ivosidenib.

#### 3.2.2 Nivolumab

Nivolumab is approved as monotherapy for multiple solid tumors (NSCLC, melanoma, RCC, HCC) and in combination with ipilimumab for melanoma and RCC at doses of 480mg IV Q4 weeks. PPK analyses have shown that the PK of nivolumab is linear with proportional exposure over a dose range of 0.1 to 10 mg/kg, and no differences in PK across ethnicities and tumor types were observed. Nivolumab clearance and volume of distribution were found to increase as the body weight increases, but less than proportionally with increasing weight, indicating that milligram/kilogram dosing represents an over-adjustment for the effect of body weight on nivolumab PK. The PPK model previously developed using data from NSCLC participants has recently been updated, using data from 1,544 participants from 7 studies investigating nivolumab in the treatment of MEL, NSCLC, and RCC.

In this dataset, the median (minimum - maximum) weight was 77 kg (35 to 160 kg) and thus, an approximately equivalent dose of 3 mg/kg for an 80-kg participant, nivolumab 240 mg q2w was selected for future studies. To predict relevant summary exposures of nivolumab 240 mg q2w, the PPK model was used to simulate nivolumab 3 mg/kg q2w and 240 mg q2w. In the simulations, the simulated participant populations consisted of 1,000 participants per treatment arm randomly sampled from aforementioned pooled database of cancer participants. Because no differences in PK were noted across ethnicities and tumor types, these simulated MEL and NSCLC data will be applicable to participants with other tumor types. The simulated measure of exposure of interest, time-averaged

concentrations for 240 mg q2w are predicted to be similar for all participants in reference to 80 kg participants receiving 3 mg/kg q2w.

Nivolumab is safe and well tolerated up to 10 mg/kg q2w dose level. AEs have been broadly consistent across tumor types following monotherapy and have not demonstrated clear dose-response or exposure-response relationships. Additionally, the simulated median and 95th prediction interval of nivolumab summary exposures across body weight range (35 to 160 kg) are predicted to be maintained below the corresponding observed highest exposure experienced in nivolumab (ie, 95th percentile following nivolumab 10 mg/kg q2w from Study CA209003). Thus, while participants in the lower body weight ranges would have greater exposures than 80 kg participants, the exposures are predicted to be within the range of observed exposures at doses (up to 10 mg/kg q2w) used in the nivolumab clinical program and are not considered to put participants at increased risk.

For participants with greater body weights, the simulated ranges of exposures are also not expected to affect efficacy because the exposures predicted following administration of a 240 mg q2w are on the flat part of the exposure- response curves for previously investigated tumors, **MEL** and NSCLC. Given the similarity of nivolumab PK across tumor types and the similar exposures predicted following administration of 240 mg flat dose compared to 3 mg/kg, it has been expected that the safety and efficacy profile of 240 mg nivolumab will be similar to that of 3 mg/kg nivolumab.

More recently, data on the clinical pharmacokinetics, safety, and efficacy of 480 mg IV over 30 min every 4 weeks has been collated and reviewed across tumor types, leading to FDA approval for the 480 mg dosing regimen. Hence, combination dosing of nivolumab for this study will be 480mg IV Q 4 weeks.

Investigational supply is being provided for this study. Please reference the nivolumab 1B for dosing information and proper storage conditions.

#### 3.3 Criteria for Study Termination

In the event of such action, written notification documenting the reason for study termination will be provided to each Local Investigator. The study will be terminated if any of the following circumstances occur: Determination of unexpected, significant, or unacceptable risk to participants. Failure to enter participants at an acceptable rate. Insufficient adherence to protocol requirements. Plans to modify, suspend, or discontinue the development of the study treatment. Other administrative reasons.

#### 4.0 Study Population

#### 4.1 Inclusion Criteria

- 1. Be:::: 18 years of age.
- 2. Have a histopathological diagnosis (fresh or banked tumor biopsy sample, preferably collected within the last 3 years) of an advanced solid tumor for which curative treatment is not available and have undergone appropriate standard of care treatment options (in the opinion of the treating investigator).
- 3. Have a documented *IDH1* gene-mutated disease (from a fresh tumor biopsy or the most recent banked tumor tissue available) based on CLIA certified sequencing (R132C/L/G/H/S mutation variants tested).

- For glioma, must have both 1) contrast enhancing disease and 2) WHO 2016 grade 2
- 4. Have an ECOG PS score of O or 1 (Appendix 11.1)
- 5. Have at least one evaluable and measurable lesion as defined by RECIST vI.1 (solid tumors) or Response Assessment in Neuro-Oncology (RANO) Criteria (glioma).
- 6. Have recovered from toxicities associated with prior anticancer therapy to baseline or :5 grade 1 unless stabilized under medical management per investigator.
- 7. Have adequate bone marrow function as evidenced by:
  - Absolute neutrophil count I,500/mm^3 or 1.5 x 10^9/L
  - Hemoglobin 8 g/dL
  - Platelets 100,000/mm^3 or 100 x 10^9/L
- 8. Have adequate hepatic function as evidenced by:
  - Serum total bilirubin :5 2 x upper limit of normal (ULN), unless considered due to Gilbert's disease
  - Aspartate aminotransferase (AST) and alanine aminotransferase (ALT) :5 5 x ULN in the presence of liver metastases (or primary hepatic tumor) OR :5 2x ULN within glioma patients
- 9. Have adequate renal function as evidenced by:
  - Serum creatinine < 1.5 x ULN OR Creatinine clearance 50 ml/min based on the Cockroft-Gault glomerular filtration rate (GFR) estimation: (140-Age) x (weight in kg) x (0.85 if female)/72 x serum creatinine
- 10. Be able to understand and willing to sign the informed consent form (or have legal representation) and to comply with scheduled visits, treatment plans, procedures, and laboratory tests, including serial peripheral blood sampling, biopsies, and urine sampling, during the study. A legally authorized representative may consent on behalf of a participant who is otherwise unable to provide informed consent if acceptable to and approved by the IRB/Independent Ethics Committee (IEC).
- 11. Female participants with reproductive potential must have negative serum pregnancy testing within 72 h prior to the initial administration of study drug, then every 4 weeks±l week, or a negative confirmation from an obstetrician in case of equivocal serum pregnancy results. Females of reproductive potential are defined as sexually mature women who have not undergone a hysterectomy, bilateral oophorectomy, or tubal occlusion or who have not been naturally postmenopausal (ie, who have not menstruated) for at least 24 consecutive months (ie, have not had menses at any time in the preceding 24 consecutive months).

Men with partners who are women with reproductive potential must agree that they or their partners will use two effective forms of contraception (including at least one barrier form) when engaging in reproductive sexual activity. Women of child-bearing potential (WOCBP) receiving nivolumab will be instructed to adhere to contraception for a period of 7 months after the last dose of nivolumab. Men receiving nivolumab and who are sexually active with WOCBP will be instructed to adhere to contraception of 7 months after the last dose of nivolumab.

Effective forms of contraception are defined as hormonal oral contraceptives, injectables, patches, intrauterine devices, intrauterine hormone-releasing systems, bilateral tubal ligation, condoms with spermicide, or male partner sterilization.

### 4.2 Exclusion Criteria

Participants who meet any of the following criteria will not be enrolled in the study:

- 1. Received a prior IDH inhibitor.
- 2. Received systemic anticancer therapy or an investigational agent< 2 weeks prior to Day 1). In addition, the first dose of study treatment should not occur before a period?: 5 half-lives (ti/2) of the investigational agent has elapsed.
- 3. For solid tumor patients: received radiotherapy to metastatic sites of disease< 2 weeks prior to Day 1 and for glioma patients have received radiation within 3 months prior.
- 4. For solid tumor patients, have underwent hepatic radiation, chemoembolization, and radiofrequency ablation< 4 weeks prior to Day 1.
- 5. Participants must not have a diagnosis of immunodeficiency or is receiving systemic steroid therapy at a dose of> 10 mg prednisone daily or equivalent at time of first dose of study treatment.
- 6. Participants must not have active autoimmune disease that has required systemic treatment in the past 2 years (i.e., with use of disease modifying agents, corticosteroids or immunosuppressive drugs). Replacement therapy (e.g. thyroxine, insulin, or physiologic corticosteroids replacement therapy for adrenal or pituitary insufficiency, etc.) is not considered a form of systemic treatment.
- 7. Participants must not have a known history of non-infectious pneumonitis that required steroids for treatment.
- 8. Participants must not have evidence of interstitial lung disease.
- 9. For solid tumor patients, have known symptomatic brain metastases requiring steroids. Participants with previously diagnosed brain metastases are eligible if they have completed their treatment and have recovered from the acute effects of radiation therapy or surgery prior to study entry, have discontinued corticosteroid treatment for these metastases for at least 1 week and have radiographically stable disease for at least 1 month prior to study entry.
- 10. Have a history of another primary cancer that is active requiring treatment, progressing or for which the treating investigator believes will make disease assessment unreliable.
- 11. Have evidence of intracranial or intra-tumoral hemorrhage either by MRI or computed tomographic (CT) scan. Participants with resolving post-surgical changes, punctate hemorrhage, or hemosiderin are eligible.
- 12. Underwent major surgery within 4 weeks of Day 1 or have not recovered from post-surgery toxicities.
- 13. Are pregnant or breastfeeding.

- 14. Are taking known strong CYP3A4 inducers or sensitive CYP3A4 substrate medications with a narrow therapeutic window (Appendix 11.2), unless they can be transferred to other medications within 2'.5 *t112* prior to dosing.
- 15. Are taking P-glycoprotein (P-gp) transporter-sensitive substrate medications with a narrow therapeutic window (Appendix 11.2), unless they can be transferred to other medications within 2'. 5 t112 prior to administration of study treatment.
- 16. Have an active infection requiring systemic anti-infective therapy or with an unexplained fever> 38.5°C within 7 days of Day 1 (at the discretion of the treating investigator) participants with tumor fever may be enrolled).
- 17. Have any known hypersensitivity to any of the components of ivosidenib or nivolumab.
- Have significant active cardiac disease within 6 months prior to the start of study treatment, including New York Heart Association (NYHA) Class III or IV congestive heart failure (Appendix 11.3); myocardial infarction; unstable angina; and/or stroke.
- 19. Have a heart-rate corrected QT interval (using Fridericia's formula) (QTcF) (Appendix 11.4) 2'. 480 ms or other factors that increase the risk of QT prolongation or arrhythmic events (e.g., heart failure, hypokalemia, family history of long QT interval syndrome). Bundle branch block and prolonged QTcF interval are permitted with approval of the PI.
- 20. Are taking medications that are known to prolong the QT interval (Appendix 11.5), unless they can be transferred to other medications within 2'. 5 t112 prior to dosing or unless the medications can be properly monitored during the study. (If equivalent medication is not available, QTcF should be closely monitored.)
- 21. Have known active hepatitis B (HBV) or hepatitis C (HCV) infections, known positive human immunodeficiency virus (HIV) antibody results, or acquired immunodeficiency syndrome (AIDS)-related illness. Participants with a sustained viral response to HCV treatment or immunity to prior HBV infection will be permitted. Participants with chronic HBV that is adequately suppressed per institutional practice will be permitted.
- 22. Have any other acute or chronic medical or psychiatric condition, including recent (within 12 months of Day 1) or active suicidal ideation or behavior, or a laboratory abnormality that may increase the risk associated with study participation or investigational product administration or may interfere with the interpretation of study results and, in the judgment of the treating investigator, would make the participant inappropriate for entry into this study.
- 23. Have known active inflammatory gastrointestinal disease, chronic diarrhea, previous gastric resection or lap band dysphagia, short-gut syndrome, gastroparesis, or other conditions that limit the ingestion or gastrointestinal absorption of drugs administered orally. Gastroesophageal reflux disease under medical treatment is allowed (assuming no drug interaction potential).
- 24. Have been committed to an institution by an order issued either by the judicial or administrative authorities.

#### 4.3 Subject Recruitment and Registration

Participants who are candidates for enrollment into the study will be evaluated for eligibility by the treating investigator to ensure that the inclusion and exclusion criteria have been satisfied and that the participant is eligible for participation in this clinical study.

## 4.3.1 Registration Procedures

When registering a participant, patients must not start protocol treatment prior to registration. The registration will be conducted using a clinical trials management system.

Registration will require the following information: 1) protocol name and number; 2) date treatment begins; 3) participant name; 4) date of birth; 5) participant hospital medical record number; 6) primary study physician; 7) confirmation of eligibility; 8) copies of the informed consent signature page; 9) verification that the informed consent was signed.

# 4.4 Subject Withdrawal Criteria

Participants have the right to withdraw from the study at any time for any reason. A participant's discontinuation of study treatment or withdrawal from the study will not jeopardize the relationship with their healthcare providers or affect their future care. Participants may choose to discontinue study treatment but agree to remain on study for follow-up contact. This decision must be recorded in writing at the study site.

Should a participant decide to withdraw, all efforts will be made to complete and report the protocol-defined study observations as completely as possible and to determine the reason for withdrawal.

# 4.4.1 Withdrawal from Study Treatment

Participants may discontinue or be discontinued from study treatment at any time. In this situation, a participant without documented progressive disease by the treating investigator should be followed for tumor assessments until the development of progressive disease and/or survival. Participants will be discontinued from study treatment for the following reasons:

- Grade 4 QTcF prolongation.
- Disease progression (participants who are, in the opinion of the treating investigator, benefiting from treatment [e.g., slow progression or immune-related response evaluation] may be allowed to continue on study treatment)
- Severe or unacceptable toxicity
- Death
- Lead Investigator decision
- Subject decision to withdraw from treatment
- Protocol violation: non-adherence to study treatments as required for evaluability (detailed in section 8.1.1) or other protocol requirements.
- Confirmed pregnancy (study therapy should be immediately interrupted based upon a positive urinary human chorionic gonadotropin [hCG] test, and permanently discontinued if confirmed by a serum -hCG test)
- Lost to follow-up

All AEs should be followed until resolution or for a period of 28 days from the last dose of study treatment, whichever is shorter. If the participant withdrew from treatment because of an AE, every

effort must be made to perform protocol-specified safety follow-up procedures. All SAEs that occur up to 100 days post last dose of nivolumab must be reported to BMS World Wide Safety.

### 4.4.2 Study Participation Termination

Participants who discontinue treatment without disease progression or death will continue to be followed for PFS every 8 weeks after the EOT Visit (±5 days) until disease progression, death, start of subsequent anticancer therapy, or withdrawal of consent until 6 months after the last enrolled patient begins treatment. Participants will be terminated from the study for the following reasons:

- Death
- Withdrawal of consent for follow-up
- Loss to follow-up
- Termination of the study

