# ii. Protocol Summary

Title	Phase II study of IDHI inhibitor ivosidenib and nivolumab in IDHI mutant gliomas and advanced solid tumors	
Short Title	Phase II of ivosidenib (AG-120) with nivolumab in IDHI mutant tumors	
Protocol Number	HCC 19-096 / CA209-8U3	
Phase	Phase II	
Methodology	Interventional trial comparing response and progression-free survival to historical data	
Methodology	Treatment groups: advanced solid tumor and select gliomas harboring an IDHI mutation	
Estimated Enrollment Period	12 months	
Estimated Study Duration	36 months	
Study Centers	The UPMC Hillman Cancer Center and Memorial Sloan-Kettering Cancer Center	
Primary Objective	
 
To describe the clinical response and six month progression-free survival of patients treated with ivosidenib in combination with nivolumab
 
	
Secondary Objectives	
 
To determine the safety of ivosidenib in combination with nivolumab
 
To summarize longitudinal clinical outcomes of patients treated with ivosidenib in combination with nivolumab
 
	
Exploratory Objective	To evaluate biomaterial-based biomarkers and determine their association with treatment response	

Primary Endpoints	
 
Response
 
Advanced Solid Tumors: Best overall response by RECIST 1.1 as detailed in (Section 11.8) 8 weeks after the initiation of treatment
 
Glioma: Best overall Response by Response Assessment in Neuro-Oncology (RANO), Criteria as detailed in (Section 11.9) 8 weeks after the initiation
 

	
 
of treatment
 
Six Month Progression-Free Survival (PFSG)         
 
All tumor types: Survival to six months after the initiation of treatment without objective tumor progression
 
 
 

Secondary Endpoints	
 
The occurrence of dose-limiting toxicity (DLT), as defined in Section 7.5, in patients receiving ivosidenib plus nivolumab.
 
Adverse Events and Serious Adverse Events related to study treatment (per CTCAE vS.0)
 
Progression-free Survival (PFS) - Survival after the initiation of treatment without objective tumor progression up until 18 months after the last participant has initiated treatment
 

Exploratory Endpoints	
 
Biomarker Studies - quantitative measures of response biomarkers by Nanostring assay (or other available technologies at the time of analysis)
 

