## 2.2.2 Secondary Endpoints

- The occurrence of dose-limiting toxicity (DLT), as defined in Section 7.5, in patients receiving ivosidenib plus nivolumab.
- Adverse events in patients receiving the combination of ivosidenib and nivolumab based on CTCAEvS.0
- Progression Free Survival (PFS) Survival with freedom from objective tumor progression from time of first treatment until up to 18 months after the last participant has initiated treatment.

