Participants may continue with their assigned study treatment until disease progression, development of unacceptable toxicity, confirmed pregnancy, death, withdrawal of consent, the participant is lost to follow-up, or the Lead Principal Investigator (PI) ends the study, whichever occurs first. For participants who are determined to be on ivosidenib upon radiographic disease progression and demonstrate clinical benefit, treating investigators, with consult from the Lead PI, may keep the participants on ivosidenib after the disease progression.

**Post-Treatment Follow-up Visit:** A Post-Treatment Follow-Up Visit for safety will occur 28 days (no more than 33 days) after the last dose of study drug. Every effort must be made to perform protocol-specified evaluations unless consent to participate in the study is withdrawn. Assessments to be performed at the Follow-up Visit are included under study assessments. If a participant's dose is interrupted for 28 days and then the participant discontinues study participation, the EOT Visit will serve as the Post-Treatment Follow-up Visit.

**PFS Follow-up:** Participants who discontinue study treatment for reasons other than disease progression or withdrawal of consent will be followed in PFS follow-up (every 8 weeks through week 48, and every 8 weeks thereafter) until documented disease progression, death, or the initiation of new cancer therapy. If a participant begins a new anticancer therapy during PFS follow-up, information on the new anticancer therapy will be collected.

**End of Study:** End of study is defined as the point in time when all participants have died, withdrawn consent, or been lost to follow-up.

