### 6.5 Efficacy Assessments

### 6.5.1 Response to Treatment

The efficacy of ivosidenib and nivolumab will be evaluated by assessing response to treatment according to RECIST vI.1 (Appendix 11.8) or RANO Criteria (Appendix 11.9) (Eisenhauer, Therasse et al. 2009).

Radiographic assessments (CT or MRI) to obtain tumor measurements are to be conducted every 8 weeks (±7 days) from CIDI, independent of dose-delays and/or dose interruptions, and/or at any time when progression of disease is suspected. CT imaging of the chest, abdomen, and pelvis (torso) with triphasic IV contrast (30 millisieverts [mSv] per scan) should be performed at baseline and on study for solid tumor patients (not glioma patients). For participants with allergy to IV iodine contrast, CT of the chest without IV contrast and MRI of the abdomen with IV contrast should be performed at baseline and on study. For patients with solid tumors, brain scans with CT (2 mSv per scan) or MRI should be performed at baseline in participants with known treated brain metastases and on study at the same imaging time points as Torso imaging.

For the glioma cohort, MRI with contrast is required for baseline and response assessments, and CT is only allowed if an MRI is contraindicated (in the view of the treating physician). Bone scans (4 mSv per scan) will be performed at baseline if disease is suspected and on study as appropriate as the same imaging time points as Torso imaging. Any ancillary findings on the radiographic assessments will be communicated to the appropriate physician for notification to the participant. The same method (CT or MRI) should be used consistently for any given participant. For participants who discontinue study drug for reasons other than disease progression, an assessment will be conducted at the EOT Visit and every 8 weeks thereafter (with the exception of those participants who initiate a new cancer therapy after discontinuing study treatment) until any of the conditions for withdrawal of study treatments are met - as detailed in 4.4.1.

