# 8.2.3 Secondary Objective: Longitudinal Clinical Outcomes

The distribution of adverse events over time (during and after Cycle 1) will be tabulated and described graphically. Surviving participants without progression will be censored as of the date of the last negative examination. Progression-free survival, defined from the beginning of treatment as survival without objective tumor progression, up until 18 months after the last efficacy-evaluable participant has initiated treatment will be characterized by the product-limit (Ka-plan-Meier} method with a 95 confidence region.

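### Section 4.4.2 stops PFS follow-up of off-treatment, progression-free participants 6 months after the last start, but the PFS endpoint and its analysis run to 18 months

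*Combined protocol and SAP*

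**What the plan says.** All of the following are in the combined protocol and SAP.

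**When follow-up stops for participants off treatment without progression**

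- Section 4.4.2 follows them every 8 weeks until progression, death, new anticancer therapy, "or withdrawal of consent until 6 months after the last enrolled patient begins treatment".
- Section 3.1 (PFS follow-up) continues "until documented disease progression, death, or the initiation of new cancer therapy", with no calendar limit. Its end-of-study definition has none either: the study ends once every participant has died, withdrawn or been lost.
- Section 4.4.1 says such a participant "should be followed for tumor assessments until the development of progressive disease and/or survival", again with no calendar limit.
- Section 6.5.1 says "an assessment will be conducted at the EOT Visit and every 8 weeks thereafter", and ends this "until any of the conditions for withdrawal of study treatments are met", pointing to the list in 4.4.1.

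**How far the PFS endpoint and its analysis run**

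- Protocol summary: "Survival after the initiation of treatment without objective tumor progression up until 18 months after the last participant has initiated treatment".
- Section 2.2.2: "from time of first treatment until up to 18 months after the last participant has initiated treatment".
- Section 8.2.3 (Kaplan-Meier): "up until 18 months after the last efficacy-evaluable participant has initiated treatment". Participants alive without progression are censored at their last negative examination.

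The protocol summary also gives a 12-month enrolment period, a 36-month study duration and participation of at most two years.

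**The concern.** The 6-month limit in 4.4.2 and the 18-month horizon of the endpoint cannot both govern the same participants. If a site applies 4.4.2, data collection for this subgroup ends a year before the analysis horizon. Scans that were not done cannot be supplied at analysis.

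Two smaller defects add to the confusion. Section 6.5.1 ends scanning of off-treatment participants by pointing to the reasons for withdrawing treatment, and someone already off treatment has met one of them. Read literally, that gives no usable stopping point. Also, 2.2.2 counts the 18 months from the last participant, while 8.2.3 counts from the last efficacy-evaluable participant.

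At stake is the late part of the PFS curve. It loses precision, and because the limit applies only to people off treatment, censoring depends on treatment status. That censoring is informative if progression runs at a different rate after treatment stops. The documents give no figure for this.

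**Working it through.** The plan states no figure for the follow-up lost, so there is none to reproduce. The check is calendar arithmetic from the plan's own inputs, followed by scenarios under stated assumptions.

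**1. Calendar arithmetic.** Enrolment is 12 months (protocol summary); uniform accrual is assumed.

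| Rule | Study month of cut-off | Potential follow-up, last to first enrolled |
|---|---|---|
| 4.4.2 | 12 + 6 = 18 | 6 to 18 months |
| Summary, 2.2.2, 8.2.3 | 12 + 18 = 30 | 18 to 30 months |

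The gap is 30 - 18 = 12 months and does not depend on the accrual pattern. Month 30 fits within the 36-month study duration. A participant enrolled at month e has potential follow-up of 30 - e months under the longer rule. This exceeds 24 when e < 6, so half of participants would pass the two-year participation limit.

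**2. Number affected.** Assumptions:

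- PFS is exponential with a median of 3.5 months (the upper bound expected in 8.2.1), 6 months (the doubling aimed at in 1.2.1) or 12 months (an added upper scenario).
- A share q of 20% or 50% stop treatment without progression by 12 months, also exponentially.
- The off-treatment to on-treatment progression hazard ratio is 0.5, 1 or 2.
- New anticancer therapy is ignored.

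At hazard ratio 1 the count has a closed form. Let λ = ln 2 / median, μ = -ln(1 - q)/12, and A(r) = (e^(-6r) - e^(-18r))/(12r). Here A(r) averages e^(-ru) over potential follow-up u from 6 to 18 months.

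- Off treatment and progression-free at month 18: 35 × [A(λ) - A(λ + μ)].
- PFS events missed among them between months 18 and 30: that count × (1 - e^(-12λ)).

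Example with median 6 and q = 0.5: λ = 0.1155 and μ = 0.0578, so A(λ) = 0.2705 and A(λ + μ) = 0.1488. The count is 35 × 0.1217 = 4.26, and events missed are 4.26 × 0.75 = 3.2.

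Simulation with 400,000 participants per scenario, scaled to 35, covers the other hazard ratios.

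| Median PFS | Affected, HR 1 (q = 20% to 50%) | Events missed, HR 1 | Affected, all scenarios |
|---|---|---|---|
| 3.5 months | 0.67 to 1.73 | 0.6 to 1.6 | 0.3 to 3.3 |
| 6 months | 1.69 to 4.26 | 1.3 to 3.2 | 0.9 to 6.3 |
| 12 months | 3.36 to 8.38 | 1.7 to 4.2 | 2.4 to 10.3 |

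**3. Effect on the Kaplan-Meier estimate.** This compares the curve with off-treatment participants capped at month 18 against the curve with everyone followed to month 30, over the same scenarios.

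| Time on the curve | Shift (capped minus full) |
|---|---|
| 6 months | 0 |
| 12 months | -0.008 to +0.010 |
| 18 months | -0.032 to +0.034 |

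At hazard ratio 1 the shift is 0 apart from simulation error. It is negative when off-treatment progression is slower and positive when it is faster.

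**4. Primary endpoint.** Under 4.4.2 the last participant's potential follow-up is exactly 6 months and everyone else's is longer. PFS6 is therefore largely unaffected.

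**The case against.** The strongest reply has five parts.

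- **Only 6 against 18 months is a direct conflict.** Sections 3.1 and 4.4.1 are merely silent on a calendar limit, and a specific limit can qualify a general rule. The wording in 2.2.2 can be read as a ceiling. This is fair as far as it goes, but a ceiling on the analysis does not explain ending collection a year earlier for one subgroup. The 6.5.1 pointer is mainly a wording fault, since the 4.4.1 list also contains progression, death and loss to follow-up.
- **The intended direction is uncertain.** The 6-month limit gives at most 18 months of follow-up and fits the two-year participation line; the 18-month horizon does not. The 36-month study duration accommodates the longer horizon. This stands, and the fix must allow for either intention.
- **The scenarios are generous.** The largest count and shift come from the 12-month median, above what the plan expects. In the single-agent cholangiocarcinoma data in 1.4.3.1, 6 of 48 (12.5%) had stopped for reasons other than progression. Length of follow-up is not given there, and nivolumab may raise the rate. With 12.5% stopping by 12 months and medians of 3.5 to 6 months, 0.2 to 1.5 of 35 are affected and the 18-month shift is at most 0.010. A simple binomial standard error at n = 35 is larger: √(0.028 × 0.972/35) = 0.03 and √(0.125 × 0.875/35) = 0.06 for the two medians at equal hazards. Ignoring new therapy also inflates the counts. These points limit the size of the effect but leave the contradiction in place.
- **Scans carry a burden.** At 30 mSv per torso CT (6.5.1), 12 months of 8-weekly imaging is 52/8, or 6 to 7 scans: 180 to 210 mSv for a solid-tumour participant. The figure is right, but 3.1 and 6.5.1 already call for these scans.
- **The two anchors may hardly differ.** The documents do not show a material gap between the last participant and the last evaluable one. That part is a matter of tidying.

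**Conclusion.** The concern holds. As written, 4.4.2 ends PFS follow-up for off-treatment, progression-free participants 12 months before the horizon in the protocol summary, 2.2.2 and 8.2.3. That gap follows from the stated limits alone. The ranges of 6-18 against 18-30 months also need the 12-month enrolment period.

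The number affected rests on the assumptions in the working, because the documents do not give it: a fraction of one participant to about six of 35 at the PFS medians the plan discusses, and up to about ten at a 12-month median. Any bias is likely small, could go either way and vanishes at equal hazards. The main harms are lost late-PFS information and conflicting instructions to the two study centres. The sample size is unchanged. This should be corrected before the earlier cut-off passes, because missed assessments cannot be recovered.

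**What to change.** Replace the 6-month limit in 4.4.2 with a rule that matches the endpoint, for example:

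> Participants who stop study treatment without progression are followed for PFS every 8 weeks until progression, death, new anticancer therapy, withdrawal of consent, loss to follow-up, or 18 months after the last participant begins treatment, whichever is first.

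Then:

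- use or cite this sentence in 3.1, 4.4.1 and 6.5.1, replacing the 6.5.1 pointer to the treatment-withdrawal list;
- align the end-of-study definition in 3.1;
- use one definition of the last participant in the summary, 2.2.2 and 8.2.3;
- change or explain the two-year participation line in the summary.

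If the sponsor does intend 6 months, restate the PFS horizon in the summary, 2.2.2 and 8.2.3 instead, and still bring 3.1, 4.4.1 and 6.5.1 into line.

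The cost is an amendment to wording. The longer horizon means up to 12 more months of scheduled 8-weekly follow-up than 4.4.2 allows, with its imaging burden, for the few participants concerned. It fits the stated study duration.
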